Protocol Component	Description under target trial	Description under Emulation
Eligibility Criteria	Adult inpatients receiving B-lactam therapy for culture confirmed monomicrobial invasive GAS between who can be randomized within 72h of index culture	Adult inpatients receiving B-lactam therapy for culture confirmed monomicrobial invasive GAS between the years 2015-2021 in the PINC AI™ dataset who receive anti-toxin within 3 days of index culture.
Treatment strategies	B-lactam therapy as primary therapy for GAS started within (+/-) 3 days of index GAS culture and continued for a minimum of 3 consecutive days. Adjunctive anti-toxin (clindamycin vs. linezolid) therapy started within (+) 3 days of culture.	Same as target trial.
Assignment procedures	
Patients will be randomly assigned within 3 days of culture (grace period) to clindamycin vs. linezolid. Investigators and patients and will be aware of the strategy to which they have been assigned (pragmatic, unblinded, open-label non-inferiority).
 
Switching between linezolid and clindamycin will not be permitted under the protocol.
	
Patients will be assigned to the anti-toxin therapy compatible with their observed treatment. Difference in baseline characteristics and confounding by indication will be addressed through the creation of a propensity weighted cohort.
 
Those who received both agents within the eligibility period will be excluded.

Follow up period	Starts at time of randomization (anti-toxin initiation) and ends at death, discharge to hospice, loss to follow up or 90 days, whichever occurs earliest.	Starts at time of anti-toxin initiation and ends at death, discharge to hospice or discharge from the hospital to home or facility or administrative censorship on Jan 31 st 2022.
Outcome	
Primary outcome: Time to all-cause mortality (or discharge to hospice) censored at 90 days.
 
Secondary outcome: infection attributable 90-day mortality, all-cause in-hospital mortality, 90-day disease reoccurrence, length of stay following anti-toxin administration among survivors, occurrence of CDI
	
Primary outcome: All-cause in-hospital mortality (or discharge to hospice)/ time to death (days).
 
Secondary outcome: Length of stay following anti-toxin administration among survivors, occurrence of CDI requiring treatment following anti-toxin administration.

requiring treatment following anti-toxin administration up to 90 days, occurrence of serotonin surge syndrome while on therapy.

Causal contrast of interest	Intention-to-treat effect; per-protocol effect.	Observational analog to Intention-to-treat effect and per-protocol effect.
Analysis plan	Intention-to-treat and per protocol effects estimated via comparison of adjusted 90 day in-hospital mortality risk assigned to each treatment strategy.	
Intention-to-treat and per protocol effects estimated via comparison of adjusted in-hospital mortality risk assigned to each treatment strategy.
 
To account for confounding by indication a propensity score (PS) will be generated based on the probability of receiving linezolid using the patient and center level variables selected a priori based on clinical judgment, . Overlap weighting on a propensity-score between the two groups will be performed with downstream adjustment for ICU stay , shock and debridement/source control.

Abbreviations: CDI: Clostridioides difficile infection; GAS: Group A streptococcus.

The study was designed in accordance with the trial emulation approach described by Hernán and Robins¹⁹. The study aims to emulate a hypothetical target pragmatic multi-center, non-blinded trial.

Eligibility

Adult inpatients patients (≥ 18 y of age) with culture confirmed proven or probable (see below) invasive monomicrobial GAS in the PINC AI™ database between 2015-2021 who receive a β -lactam for a minimum of 3 days within 3 days of culture will be eligible for inclusion in the emulated trial. Patient will be included if they then receive anti-toxin therapy within 3 days of culture being drawn, as long as B-lactam therapy has been initiated prior or on the same day as antitoxin therapy.

Proven and probable invasive GAS definitions will be adapted from the CDC ABCs case definition (<https://www.cdc.gov/abcs/methodology/case-def-ascertain.html>) using a previously used algorithm compatible with EHR data which incorporates ICD-codes³. Proven invasive GAS infection will be defined as GAS isolated from a normally sterile site, such as blood, cerebrospinal fluid, pleural fluid, peritoneal fluid, pericardial fluid, bone, joint/synovial fluid, or internal body site (e.g., lymph node, brain) OR GAS isolated from a wound culture and accompanied by necrotizing fasciitis or streptococcal toxic shock syndrome. Probable invasive GAS infection is defined as the isolation of GAS from a non-sterile site in patients with either an ICD-10 code that matches the clinical infection syndrome (eg ICD-10 for lower respiratory infection and BAL culture with GAS) or a non-specific streptococcal infection code. These include lower respiratory, musculoskeletal, genitourinary and/or skin and soft tissue samples as well other miscellaneous deep-seated infections (eg retropharyngeal abscess). Previously identified ICD-9 codes³ will be cross walked to ICD-10 codes manually with additional manual de-novo search for compatible ICD-10 codes. Final codes and culture site classification will be adjudicated by two infectious diseases clinicians.

Inclusion Criteria

- Adult inpatients patients (≥ 18 y of age)
- Monomicrobial Group A streptococcus invasive infection
- Primary therapy with a B-lactam agent (initiated before or on same day as adjunctive anti-toxin therapy)

Exclusion Criteria

Patient will be excluded if they have any of the following :

- Patients with a polymicrobial GAS culture
- Patients who allocated to the linezolid arm but have a documented linezolid resistant isolate
- Patient with concomitant MSSA/MRSA invasive infection (+/- seven days of index GAS eligibility culture)
- Patients who receive both anti-toxin agents (violation of protocol)
- Patient who don't complete at least 3 days of B-lactam (violation of protocol)

Primary Outcome measure:

in-hospital mortality defined as death during hospitalization or discharge to hospice.

Secondary outcome measures:

- Length of stay among survivors

- *Clostridioides difficile* infection
 - Description: *C. difficile* positive (PCR or antigen) result within same encounter downstream of the antitoxin therapy within 30 days and/or presence of a non present on admission (POA) *C. difficile* diagnosis code in conjunction with receipt of *C. difficile* therapy (PO/rectal vancomycin or PO fidaxomicin or IV metronidazole)

Statistical Analysis Plan

To account for confounding by indication a propensity score (PS) will be generated based on the probability of receiving linezolid using the patient and center level variables. Variables thought to be associated with a clinician's decision to initiate adjunctive treatment with linezolid (vs. clindamycin) and with mortality will be selected for inclusion. Overlap weighting on a propensity-score between the two groups will be performed with downstream adjustment for ICU stay, shock and debridement/source control. To take the clustered data structure into account, matching on center will be attempted if feasible, if not, propensity scores will be calculated using a mixed effects model with hospital as a random effect. Covariate balance between the two groups before and after generation of the weighted cohorts will be assessed by examining the standard mean difference for variables across the exposure categories.

Power calculation

Because no randomized clinical trials have previously compared adjunctive treatment options for GAS, the sample size estimation was derived from the largest retrospective study available³. In that study the overall in hospital mortality in adjunctive clindamycin group 6.5% in the propensity matched cohort. A published abstract, the only other published clinical data on the topic, found mortality between linezolid (n=26) and clindamycin (n=26) groups to be similar (clindamycin 11.5% and linezolid 7.7%)²¹. This was confirmed by preliminary exploration of GAS blood stream infection cases in our dataset (clindamycin 10%, linezolid 12%).

Based on a mortality rate of 6.5% in the both groups as the most conservative estimate and a noninferiority margin of 5% with 1:4 allocation ratio, 1035 patients (828 clinda + 207 Linezolid) will be needed in total to achieve 80% power with a 2-sided α level of 0.05, allowing for 10% dropout. A 5% noninferiority margin was chosen as the maximal difference in mortality between treatments that would be clinically acceptable, by consultation with infectious disease, critical care specialists within the study team.

Statistical analysis will be performed with R using Rstudio V2022.12.0.353 (R Foundation for Statistical Computing, Vienna, Austria). The reporting of the study will be in line with Strengthening the Reporting of Observational Studies in Epidemiology (STROBE) reporting guidelines²⁰

Sensitivity analysis

The following sensitivity analysis will be performed:

- Analysis of patients with proven GAS only (excluding those with probable GAS)
- Analysis where hospital as a random effect is not included
- An analysis which includes those who receive anti-toxin +/-3 days of index therapy to capture those treated empirically prior to culture results.
- An analysis without PS weighting and only downstream logistical regression (as would be done in a classical observational study).
- An analysis utilizing cloning methodology to account for potential immortal time bias²¹

Subgroup Analysis

We will use similar methods as for the primary analysis to assess the impact of allocation to either treatment group on the following prespecified subgroups

- Patients with NSTI or TSST
- Patients with pressor dependent shock
- Patients admitted to the ICU within one day (+/-) of index GA eligibility culture
- Excluding patients with who received clindamycin that had a clindamycin non-susceptible isolates (defined as resistant or intermediate or a positive D-test)
- Excluding patients with who received clindamycin that had a clindamycin non-susceptible isolates or had clindamycin antimicrobial susceptibility testing missing
- Stratified by days of anti-toxin therapy (>1, >2, >3 days)

Missing Data Plan

Less than 5% missingness across key variables is expected

References

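### The NSTI/TSS and ICU subgroups, and the wound-culture route to proven GAS, do not require the condition to be present by anti-toxin start, so events after treatment begins can affect who is in them

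*Combined protocol and SAP*

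**What the plan says.** Table 1 (Follow up period, emulation column) sets time zero: follow-up "Starts at time of anti-toxin initiation and ends at death" or another listed end point. Anti-toxin may start on the day of culture or up to 3 days later (Table 1; Eligibility).

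The Eligibility section gives two routes to proven disease. The first rests on the culture site alone: "Proven invasive GAS infection will be defined as GAS isolated from a normally sterile site, such as blood" or another sterile site. The second is "GAS isolated from a wound culture and accompanied by necrotizing fasciitis or streptococcal toxic shock syndrome". No window is given for the second route relative to culture, admission or anti-toxin start. The syndromes come from an algorithm that uses ICD codes, and no present-on-admission (POA) or date rule is stated for them. Other non-sterile cultures fall into the lower class: "Probable invasive GAS infection is defined as the isolation of GAS from a non-sterile site in patients with either an ICD-10 code" for the matching syndrome, or a non-specific streptococcal code.

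Three analyses use these or similar conditions:

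- The Sensitivity analysis section lists an analysis restricted to proven cases.
- The Subgroup Analysis section lists "Patients with NSTI or TSST", with no time limit.
- The same section lists "Patients admitted to the ICU within one day (+/-) of index GA eligibility culture", a window tied to culture and not to anti-toxin start.

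Elsewhere the plan does fix timing: 7 days either side of culture for the MSSA/MRSA exclusion, and POA status in the definition of *C. difficile* infection.

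**The concern.** In the target trial, a subgroup would be fixed at randomization. In the emulation the equivalent moment is anti-toxin start. A subgroup that admits patients on the strength of something that happened later is conditioned on a post-treatment variable.

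That matters here because the Significance and Background section says both drugs inhibit toxin and virulence-factor production. Necrotizing fasciitis (NF) or streptococcal toxic shock syndrome (STSS) arising after the first dose could therefore depend on which drug was given. If it does, the two arms of the subgroup hold different mixes of baseline and late cases. Overlap weights built on baseline covariates balance the arms at time zero. They do not balance who progresses afterwards.

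At stake are the NSTI/TSS and ICU subgroup results and, to a lesser extent, the proven-only analysis. The background section names severe invasive GAS and NSTI as the setting in which adjunctive clindamycin is recommended, so readers are likely to look closely at these results.

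**Working it through.** **Timing of each definition against time zero**

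| Definition | Time limit in the plan | Can an event after anti-toxin start bring a patient in? |
|---|---|---|
| Proven, sterile site | Culture site only | No |
| Proven, wound culture | None for NF/STSS | Yes |
| NSTI/TSS subgroup | None | Yes |
| ICU subgroup | Culture day, plus or minus 1 | Yes, if anti-toxin starts on day 0 and ICU admission is on day +1; unclear if both fall on day +1 |
| Primary cohort | Proven and probable together | Not shown: a wound-culture patient without NF/STSS can still enter as probable |

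**Size of the effect on the NSTI/TSS subgroup**

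The plan states no figure to reproduce and gives no onset rates. Every input below is an assumption.

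- Share of patients with NF/STSS at time zero: b = 10%.
- Their mortality: 25% in both arms, so the true baseline-subgroup difference is 0.
- Later progression among the rest: q = 5% on clindamycin and 10% on linezolid.
- Mortality of late cases: m = 15%, 25% or 40%, the same in both arms.

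Mortality in the any-time subgroup of one arm is

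(b × 0.25 + (1 − b) × q × m) / (b + (1 − b) × q).

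Denominators: clindamycin 0.10 + 0.90 × 0.05 = 0.145; linezolid 0.10 + 0.90 × 0.10 = 0.190. Late cases are then 0.045/0.145 = 31.0% of the clindamycin subgroup and 0.090/0.190 = 47.4% of the linezolid subgroup.

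| m | Clindamycin | Linezolid | Linezolid minus clindamycin |
|---|---|---|---|
| 15% | 0.03175/0.145 = 21.90% | 0.0385/0.190 = 20.26% | -1.63 points |
| 25% | 0.03625/0.145 = 25.00% | 0.0475/0.190 = 25.00% | 0 |
| 40% | 0.0430/0.145 = 29.66% | 0.0610/0.190 = 32.11% | +2.45 points |

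The same result follows from a short form: difference = (m − 0.25) × (late share on linezolid − late share on clindamycin). For m = 40% this is 0.15 × (0.4737 − 0.3103) = 0.0245.

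**Smaller contrast in progression.** With 5% versus 6%, the linezolid denominator is 0.10 + 0.054 = 0.154 and its late share is 35.1%. The differences become (0.0331/0.154) − 21.90% = -0.40 points at m = 15%, and (0.0466/0.154) − 29.66% = +0.60 points at m = 40%.

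**A second set of assumptions.** Take b = 30% with 12% baseline mortality in both arms. Late shares at 5% versus 10% progression are 0.035/0.335 = 10.4% and 0.070/0.370 = 18.9%. With late-case mortality of 20% or 30%, the differences are 0.08 × 0.0847 = +0.7 and 0.18 × 0.0847 = +1.5 points. At 10% versus 20% progression they are +1.0 and +2.3 points. Swapping the arms reverses the sign.

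**When it vanishes.** The difference is zero if progression and late-case mortality are both equal across arms. It is also zero if late cases die at the same rate as baseline cases.

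No size can be given for the ICU subgroup or the proven-only analysis. The documents give neither the frequency of day +1 ICU admission after a day 0 start nor the wound-culture share of proven cases.

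**The case against.** The strongest reply is that the plan takes its case definition from an algorithm used in an earlier study, which may carry its own timing rule, and that the wording of the wound-culture route points to concurrence with the culture. Both are fair. But the plan states no such rule, and concurrence with culture would still not be concurrence with anti-toxin start. If a rule exists, stating it resolves the NF/STSS part.

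It can also be said that the figures rest wholly on assumption and that a doubling of progression is a strong one. That stands: at 5% versus 6% the shift is well under a point.

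The ICU point is narrower than the NF/STSS point, because a window exists and only early starters are exposed. That also stands, but the stated window does admit entry after time zero.

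A reader might infer more than the documents support:

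- **That late complications decide who is in the proven-only cohort.** Sterile-site patients are proven whatever happens later. Only the wound-culture route is open.
- **That the primary result is biased.** Reclassification from probable to proven leaves the patient in the main cohort.
- **That the drugs are given to prevent NF or STSS.** The documents speak of reducing toxin production and of managing severe disease and NSTI. Toxin suppression makes an effect on progression plausible, and the point needs no more than that.
- **That the subgroup would hide a real harm.** Under the first set of assumptions with m = 25%, and 3% mortality in patients who do not progress, the difference across all wound-culture patients is 0.90 × 0.05 × (0.25 − 0.03) = +0.99 points while the subgroup shows 0. These are different populations. The baseline subgroup's true difference is 0, so the subgroup answer is correct there, and the corrected definition would show 0 too.

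**Conclusion.** The point holds for the two subgroups and, to a lesser extent, for the proven-only sensitivity analysis. As written, the plan lets conditions that arise after anti-toxin start affect membership, and the baseline weights cannot undo this. Neither direction nor size can be determined from the documents.

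Under the assumptions shown, a true NSTI/TSS subgroup difference of 0 appears as anything from -1.6 to +2.5 points with a doubling of progression, and from about -0.4 to +0.6 with a small difference in progression. For scale, the noninferiority margin in the Power calculation section is 5 points. This should be corrected before analysis, but it does not put the primary comparison in doubt.

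**What to change.** Add one sentence to the case definition and amend two lines of the subgroup list.

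- For proven status by wound culture and for the NSTI/TSS subgroup, count NF, STSS or NSTI only if it is coded present on admission or supported by dated evidence on or before the anti-toxin start day. Later onset leaves the patient in the class held at baseline.
- Define the ICU subgroup by ICU status on or before the anti-toxin start day, in place of the window around culture.
- If the earlier algorithm already contains a timing rule for NF/STSS, write it out and check it against anti-toxin start.

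The plan already relies on POA status for *C. difficile* infection, so the data element is not new to it. The cost is a somewhat smaller proven-only cohort and somewhat smaller subgroups, hence wider intervals. If only calendar days are available, the order of events on the start day itself stays unresolved, which is a much smaller gap than the present one.

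### The linezolid-resistance exclusion applies to the linezolid arm only, so eligibility for the primary cohort depends on the treatment received

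*Combined protocol and SAP*

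**What the plan says.** The Exclusion Criteria list "Patients who allocated to the linezolid arm but have a documented linezolid resistant isolate". The criterion gives no date limit and does not tie the isolate to the index culture.

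Table 1 defines the arm in the emulation by what was given: "Patients will be assigned to the anti-toxin therapy compatible with their observed treatment". The anti-toxin window is counted from the culture draw. The Eligibility section says "Patient will be included if they then receive anti-toxin therapy within 3 days of culture being drawn", and Table 1 says "Adjunctive anti-toxin (clindamycin vs. linezolid) therapy started within (+) 3 days of culture". Follow-up "Starts at time of anti-toxin initiation and ends at death, discharge to hospice" or the other listed end points, so time zero is the first anti-toxin dose. The contrast is "Observational analog to Intention-to-treat effect and per-protocol effect".

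Clindamycin resistance is handled elsewhere and differently. It is not in the Exclusion Criteria. Under Subgroup Analysis one item reads "Excluding patients with who received clindamycin that had a clindamycin non-susceptible isolates (defined as resistant or intermediate or a positive D-test", and a second item also drops clindamycin-treated patients with no clindamycin susceptibility result.

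**The concern.** Target trial emulation rests on one eligible population, defined before or at time zero without reference to the arm. Here two patients with the same linezolid-resistant isolate are handled differently: the one given clindamycin is analysed and the one given linezolid is removed. A randomised trial could not apply such a rule at entry, because the arm is not yet known.

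The handling is also one-sided. In the primary comparison, patients whose isolate is known to resist their adjunct are taken out of the linezolid arm but left in the clindamycin arm. The target trial is framed as non-inferiority and the study is sized on a 5% margin. If resistant cases die more often, the asymmetry lowers observed linezolid mortality and so favours the claim under test. The estimate is then not the effect of starting linezolid rather than clindamycin in a common population.

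**Working it through.** **1. Does eligibility depend on the arm?** The criterion applies to the linezolid arm, and the arm is the drug received. A patient with a documented linezolid-resistant isolate is therefore excluded if given linezolid and included if given clindamycin. This follows from the Exclusion Criteria and Table 1 read together.

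**2. Is there a matching rule for clindamycin?** No. Clindamycin non-susceptibility removes patients only in the two Subgroup Analysis items.

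**3. Does anything planned repair it?** Overlap weighting acts on the patients who remain and cannot restore those removed from one arm. None of the five listed sensitivity analyses is described as reinstating them. Two other exclusions are labelled protocol violations. This one is not, and it shapes the cohort for the intention-to-treat analog as well as for the per-protocol effect.

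**4. Timing.** Anti-toxin starts 0 to 3 days after the culture is drawn. For a start on the day of the draw, a susceptibility result from that culture must come after time zero. For starts on days 1 to 3 it could come before or after. The documents do not say when results are reported. What can be said is that the rule has no time limit, so a later result can decide eligibility.

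**5. Size.** Inputs from Power calculation: mortality p = 6.5% in both groups, margin 5 points, 828 clindamycin and 207 linezolid patients.

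The plan's sample size reproduces first. With unpooled variance, the clindamycin group is 0.065 × 0.935 × (1 + 4) × (1.645 + 0.842)² / 0.05² = 752, and linezolid is 752/4 = 188. Multiplying by 1.1 gives 828 + 207 = 1035. This match needs 0.05 used one-sided, although the text calls it 2-sided. That is a separate matter and does not affect this point.

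Not in the documents, so assumed:
- q, the share of linezolid-arm patients with a documented resistant isolate: 0.1% to 5%.
- m, mortality in those patients: 11.5% (p plus the margin), 19.5% (three times p) and 25% (a high value).

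If mortality in the whole linezolid arm is p, mortality after the exclusion is (p − qm)/(1 − q). The shift is −q(m − p)/(1 − q). For example, q = 5% and m = 25% gives (6.5 − 1.25)/0.95 = 5.53%, a shift of −0.97 points.

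Shift in linezolid mortality, percentage points:

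| q | Removed of 207 | m = 11.5% | m = 19.5% | m = 25% |
|---|---|---|---|---|
| 0.1% | 0.2 | −0.005 | −0.013 | −0.019 |
| 0.5% | 1.0 | −0.025 | −0.065 | −0.093 |
| 1% | 2.1 | −0.051 | −0.131 | −0.187 |
| 2% | 4.1 | −0.102 | −0.265 | −0.378 |
| 5% | 10.4 | −0.263 | −0.684 | −0.974 |

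The most extreme cell is 0.974/5 = 19% of the margin. At q = 1% the range is 1% to 4% of it. For scale, the unweighted standard error of the difference at the planned numbers is √[0.065 × 0.935 × (1/828 + 1/207)] = 1.9 points.

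The sign depends on m. At m = 6.5% the shift is zero, and below that it reverses.

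**The case against.** The strongest defence is that the effect is likely to be small and may be zero. With rare resistance the rule touches a handful of patients, and the shift is well inside sampling error. That stands, and it sets the weight of the point.

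The comparator side is also partly covered. The two clindamycin-susceptibility analyses, run on a cohort already without linezolid-resistant patients in the linezolid arm, compare the drugs with documented resistance to the received drug removed from both. Keeping clindamycin-resistant patients in the primary comparison fits the stated motivation, since the Background cites rising clindamycin resistance. Both remarks are fair, but neither justifies an arm-specific rule in the primary cohort.

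Four stronger readings are tempting and are not supported:

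- A reader might infer that the resistance result is always obtained after treatment starts. The documents do not say when results arrive, and resistance of the index isolate is a pre-treatment property even when reported later.
- A reader might infer that the bias always runs toward non-inferiority. That holds only if resistant cases have higher mortality, on which the documents give no figure.
- A reader might infer that excluded patients were on wholly inactive treatment. Every patient receives a β-lactam as primary therapy, and resistance affects only the adjunct.
- Table 1 gives target-trial eligibility as "Adult inpatients receiving B-lactam therapy for culture confirmed monomicrobial invasive GAS between who can be randomized within 72h of index culture", with no resistance criterion, and a reader might take this as proof that the emulation departs from its target. The table is headed as a summary, and the MSSA/MRSA exclusion is missing from that row too, so this is weak evidence.

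**Conclusion.** The point holds as an inconsistency in how the primary cohort is defined. Eligibility depends on the treatment received, the two drugs are handled differently, and nothing planned undoes it. This conclusion comes from the text alone and does not depend on the timing of results or on any assumed rate.

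The numerical consequence is probably small: from about zero to just under 1 point over the assumed ranges, and zero if there are no documented resistant isolates in the linezolid arm. The direction, toward non-inferiority, is conditional on higher mortality in resistant cases. The calculation is unweighted and takes 6.5% as mortality in the linezolid arm before exclusion. It is a minor correction, worth making because a shared eligibility rule is basic to the design and the change is easy.

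**What to change.** Delete the linezolid-resistance criterion from the Exclusion Criteria, so that both arms of the primary cohort share one rule and resistance to either drug is treated alike there. Place the linezolid-resistance exclusion in a sensitivity analysis beside the two clindamycin-susceptibility analyses. Apply it to both arms only if linezolid susceptibility results exist in both. The documents do not say whether clindamycin-treated patients were tested. If they were not, restrict it to the linezolid arm and report it as an arm-dependent restriction. State how many patients it removes.

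The primary change is one line of wording and needs no new data. The downside is that a few patients with resistant isolates stay in the linezolid arm, which may be slightly less favourable to linezolid. The two-arm version of the sensitivity analysis carries the further cost of confirming that comparable testing exists.

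### Patients who receive the second anti-toxin agent after time zero are removed from the cohort, under two conflicting rules, so it cannot give the intention-to-treat analogue that the plan lists

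*Combined protocol and SAP*

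**What the plan says.** Time zero in the emulation is the start of the anti-toxin. Table 1, Follow up period: "Starts at time of anti-toxin initiation and ends at death, discharge to hospice or discharge from the hospital to home or facility". The window for starting it is set under Eligibility: "Patient will be included if they then receive anti-toxin therapy within 3 days of culture being drawn".

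Two places deal with receipt of both agents:

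- Exclusion Criteria: "Patients who receive both anti-toxin agents (violation of protocol". No time limit is attached.
- Table 1, Assignment procedures (emulation column): "Those who received both agents within the eligibility period will be excluded".

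For the target trial, the same row of Table 1 says: "Switching between linezolid and clindamycin will not be permitted under the protocol". It does not say that a randomised patient who switches leaves the analysis. In the emulation the arm is set by what was given: "Patients will be assigned to the anti-toxin therapy compatible with their observed treatment". The contrast of interest is "Observational analog to Intention-to-treat effect and per-protocol effect", and neither effect is named as primary.

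The propensity score in the Statistical Analysis Plan models the choice of linezolid over clindamycin at initiation. No section describes censoring or weighting for a later change of agent, or defines separate populations for the two effects.

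**The concern.** Under intention-to-treat, a patient who changes agent after assignment is a deviation and stays in the arm assigned. Here such a patient is treated as never having entered. Membership of the cohort then depends on something that happens during follow-up and that may be related both to the first agent and to prognosis. Weighting on baseline covariates does not correct selection on a later event.

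Because the rule is an eligibility criterion, it governs both effects. Under the Exclusion Criteria wording no switcher remains, so the two effects cannot differ in how they treat switching. Under the Table 1 wording, patients who change agent after the window stay in, but no rule says which arm they belong to or how the per-protocol analysis treats them.

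At stake is a risk difference judged against a 5-point margin. If the deleted patients differ between arms in number or in risk, the difference moves for reasons unrelated to the drugs.

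**Working it through.** **1. The rules side by side.** I read the eligibility period in Table 1 as the 3-day window given under Eligibility.

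| Patient | Exclusion Criteria | Table 1 | Timing of the event |
|---|---|---|---|
| Starts both agents on the same day, within the window | out | out | at time zero |
| Starts one agent, receives the other later within the window | out | out | after time zero |
| Starts one agent, receives the other after the window | out | in | after time zero |

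The third row is the contradiction. The second row, and the third under the Exclusion Criteria, are removals on a post-baseline event. The first row is an ordinary baseline exclusion and is not part of the problem.

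**2. The plan's own figure.** Inputs from Power calculation: 6.5% mortality in both groups, margin 5 points, 1:4 allocation, 80% power, 10% dropout. With one-sided alpha 0.05:

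n(clindamycin) = 0.065 × 0.935 × (1 + 4) × (1.645 + 0.842)² / 0.05² = 751.5, so 752, with 188 on linezolid (940 in all).

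Multiplying by 1.10 gives 828 + 207 = 1035, the stated total. At one-sided 0.025 the total would be 1314 to 1327, depending on how dropout is applied. That mismatch is a separate matter. I use 752 + 188 and one-sided 0.05 below because they reproduce the plan.

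**3. Effect of deletion.** Let p be mortality among all starters in an arm, s the share who switch and r the mortality of switchers. Mortality after deletion is (p − s·r)/(1 − s). The documents give no s or r, so every value of these is an assumption. With p = 6.5% in both arms the true difference is 0. Shifts are linezolid minus clindamycin, in points.

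| Assumed switching | Clindamycin | Linezolid | Shift |
|---|---|---|---|
| 10% in each arm, r = 13% | 5.78% | 5.78% | 0.00 |
| 10% of clindamycin only, r = 13% | (0.065 − 0.013)/0.9 = 5.78% | 6.50% | +0.72 |
| 10% of clindamycin only, r = 3.25% | 6.86% | 6.50% | −0.36 |
| 10% of linezolid only, r = 13% | 6.50% | 5.78% | −0.72 |
| Clindamycin 20%, linezolid 5%, r = 13% | 4.87% | 6.16% | +1.28 |
| Clindamycin 5%, linezolid 20%, r = 13% | 6.16% | 4.87% | −1.28 |
| Clindamycin 10% at 15%, linezolid 5% at 2% | 5.56% | 6.74% | +1.18 |
| Clindamycin 20% at 15%, linezolid 5% at 2% | 4.38% | 6.74% | +2.36 |
| Clindamycin 10% at 2%, linezolid 5% at 15% | 7.00% | 6.05% | −0.95 |

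**4. Effect on the noninferiority decision.** This uses the normal approximation with unpooled variance, with 752 + 188 patients before deletion.

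- True difference 0: the chance of declaring noninferiority is 80.0% with no deletion. It is 68.6% if 10% of clindamycin starters switch at twice the mortality and are deleted, and 88.6% if 10% of linezolid starters do.
- True difference at the margin (11.5% against 6.5%): the false-noninferiority rate is 5.0% with no deletion. Deleting 10% of starters at twice their arm's mortality makes it 12.9% (linezolid only), 2.7% (clindamycin only) or 7.7% (both arms). In the last case the apparent difference is 10.22 − 5.78 = 4.44 points, so matched switching shares and relative risks cancel only at the null.

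**The case against.** The strongest reply is that nothing in the documents shows a bias. They give no switching rate, no reasons for switching and no mortality among switchers. Matched switching gives no shift at the null, and the larger shifts above need risks of 15% and 2% in opposite arms. That stands. A reader might infer that the comparison is biased, or biased in a known direction; the documents support only that it is open to bias.

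Under Table 1 the affected group is also limited to second-agent use within 3 days of culture, and same-day receipt is a legitimate baseline exclusion. Both narrow the problem without removing it.

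Four further readings go too far:

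- That early deaths always stay in because they cannot switch. The Exclusion Criteria also remove patients who do not complete 3 days of beta-lactam, which takes out many early deaths. Some may remain, since Table 1 lets the beta-lactam start up to 3 days before culture.
- That the main analysis loses clindamycin failures due to resistance. Patients with non-susceptible isolates who stayed on clindamycin remain in; two analyses under Subgroup Analysis remove them. Only those who also received linezolid are lost.
- That intention-to-treat is the promised primary contrast. Table 1 lists both effects without ranking them.
- That the sensitivity analyses rule out any recovery of switchers. The cloning analysis comes nearest. Its stated aim is immortal time bias and its cohort is not defined, so the documents show neither that it restores switchers nor that it does not.

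**Conclusion.** The point holds as a defect of definition. The two exclusion rules conflict. Each removes some patients for an event after time zero: at any time under the Exclusion Criteria, within the 3-day window under Table 1. The cohort therefore cannot give the listed intention-to-treat analogue. It does not give a sound per-protocol effect either, because switchers are deleted from the outset instead of contributing follow-up until the switch.

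How far the result would move is unknown. With 10% of one arm switching at twice the mortality, the shift is about 0.7 points of a 5-point margin, in either direction. The more extreme assumed inputs give about 1 to 2.4 points. These sizes rest wholly on assumed switching shares and risks.

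Keeping switchers would not by itself complete an intention-to-treat analogue. The 3-day beta-lactam completion rule can also be failed after time zero and needs the same review.

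**What to change.** Put one analysis rule in both Table 1 and the Exclusion Criteria:

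1. Assign each patient to the first anti-toxin received within the eligibility window. Exclude only patients whose two agents start on the same day.
2. For the intention-to-treat analogue, keep later switchers under their first agent.
3. For the per-protocol effect, censor at the switch and apply inverse-probability-of-censoring weights, using severity and susceptibility results recorded before the switch.
4. Report the number and direction of switches by arm, with mortality by first agent.
5. Keep the current cohort, which drops everyone who received both agents, as a sensitivity analysis. State which patients enter the cloning analysis.
6. Review the beta-lactam completion criterion as an analysis rule in the same way, stating for each effect how patients who fail it after time zero are handled.

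The cost is SAP wording, a re-run of the cohort query and one censoring model, with no new data source. The planned total of 1035 does not change. The drawback is that keeping crossovers may dilute the intention-to-treat contrast toward the null, which in a noninferiority comparison can favour the conclusion sought. The per-protocol result should therefore be reported beside it.
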